5.5 End of study

5.5.1 Study Completion Procedures

Subjects will be considered to have completed the study when they have completed all examinations up to and including the Month 60 visit.

5.5.2 Log of Exit from the Study

A subject exit form must be completed for each subject who exits the study for any reason, indicating whether the subject is withdrawing (providing the reason if available), is terminated from the study, or is considered lost-to-follow-up. Before a subject is considered “lost-to-follow-up”, there must be three documented attempts to reach him. At least one of these attempts must be in writing by certified/return receipt mail, a copy of which must be included in the subject’s medical/clinic chart.

5.5.3 Exit from the Study

Subjects will have the right to withdraw from participation in the study at any time, for any reason.

Subjects may be withdrawn from the study at the discretion of the Investigator only if continuation will jeopardise the subjects’ health and/or welfare. Every effort must be made to follow withdrawn subjects for safety reasons using the appropriate CRFs until the planned end of the study period.

5.5.4 Subject withdrawal

The criteria for terminating participation in the study are detailed below:

1. Serious adverse event that is study-related (see definition further below), as recommended by the Investigator, patients with grade 3 or 4 adverse events following their initial treatment who have evidence of treatable prostate cancer on month 3 biopsy will not undergo re-treatment, will be withdrawn from the study and proceed with standard of care unless justification for continuing on study is specifically sought and approved from the IRB.
2. Subject withdrawal: at any time, a subject can withdraw from the study at his request or on the basis of the Investigator's clinical judgment.
3. Patients with evidence of clinical deterioration on the same side such as Gleason grade 5 cancer, more than 2 sextants including Gleason grade 4 cancer on the treated side on the 3-month re-biopsy will be withdrawn from the study and proceed with standard care.
4. Major protocol violation, defined as any violation that may impact the safety of a study subject.
5. Termination of the study by the Sponsor.

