This study is a phase IIb trial using optimal dose of TOOKAD® Soluble and optimal light-energy level conditions that were determined in previous phase I and II studies and confirmed by the phase III studies among patients with localized prostate cancer. Partial gland ablation therapy using thermal approaches, as an alternative to radical treatments for low-volume prostate cancer, is a treatment option currently being offered to men with prostate cancer in the U.S. as a tailored means to manage their disease with fewer side effects. Previous studies of TOOKAD® Soluble treatment have suggested that this non-thermal approach is an effective therapeutic strategy to achieve ablation of the prostatic tissue that contains the cancer lesion in this patient population. Considering the available clinical data, a phase IIb is considered appropriate at this stage, with the main aim of confirming, in intermediate risk patients, previous findings in low and favorable intermediate risk prostate cancer patients. Moreover, a single center design was also considered appropriate, as it allows for optimal standardization of the technique and better control over data acquisition.

NUMBER OF PATIENTS:

In order to obtain at least 44 evaluable patients, a total of 50 patients will be included and will be treated with TOOKAD® Soluble VTP in this study.

DRUG DESCRIPTION AND PREPARATION:

TOOKAD® Soluble - padeliporfin di-potassium (WST11) Drug Product is a dark coloured powder for solution for injection. It is packaged in amber glass vials. It is manufactured in two different presentations:

- 200 mg TOOKAD® Soluble in a 30 mL vial with blue flip-off cap, to be reconstituted, just before administration, with 20 mL of 5% dextrose solution for injection
- 400 mg TOOKAD® Soluble in a 50 mL vial with white flip-off cap, to be reconstituted, just before administration, with 40 mL of 5% dextrose solution for injection

The two presentations have the same formulation which is produced in exactly the same process and they differ only in the amount of TOOKAD® Soluble per vial, the size of the vial and the colour of the flip-off cap.

For both presentations the final concentration of TOOKAD® Soluble solution to be injected is 10 mg/mL.

INCLUSION CRITERIA:

Subjects will be eligible for inclusion in the study if all of the following criteria are met:

1. Men over 18 years of age.

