The pivotal European randomized phase III study demonstrated the benefit of TOOKAD® Soluble VTP compared to active surveillance. The analysis met both co-primary efficacy endpoints; TOOKAD® Soluble VTP significantly doubled time to progression from low-risk to moderate or high-risk prostate cancer (from 14.1 to 28.3 months; $p < 0.001$), significantly reduced the defined failure rate within 24 months after treatment (HR = 0.34; $p < 0.001$), and increased the probability of a negative biopsy at 24 months by 3.62 times (from 13.5 to 49.0%; $p < 0.001$). The robust quality of these outcomes was evidenced by the consistency of results across all 3 analysis populations (ITT, mITT, PP) and the 2 disease status subgroups (unilateral disease or bilateral disease).

Secondary efficacy endpoints also demonstrated the advantages of TOOKAD® Soluble VTP to active surveillance. The strongly positive and statistically significant ($p < 0.001$) effect of TOOKAD® Soluble VTP on the objective of focal therapy, i.e., reduction of tumour burden, indicates that the effect on disease progression may continue beyond the 24 months observed in this study. Substantial reduction in need for radical therapy, occurrence of T3 prostate cancer, and metastatic disease provide meaningful clinical outcomes for men with low-risk, localised prostate cancer.

TOOKAD® Soluble VTP resulted in a safety profile similar to the comparator in this study, active surveillance, and potentially superior to radical therapy, the alternative for management of low-risk prostate cancer. The AE profile of TOOKAD® Soluble VTP was similar to that of active surveillance except for events specifically related to the drug itself, the delivery device, or the procedure. Most of these related AEs were expected and occurred during the procedure or in the days after the procedure and resolved without sequelae. The numbers of subjects experiencing an AE related to the drug, device, or procedure (78.7%) or an SAE related to the drug, device, or procedure (15.2%) are reasonable considering the invasive aspects of this minimally invasive procedure. Urinary function and erectile function were well maintained with only transient increase in associated symptoms after the procedure. The safety profile for TOOKAD® Soluble VTP compares very favourably with radical therapies, particularly with regard to the preservation of erectile function.

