7 OUTCOMES ASCERTAINMENT

7.1 Prostate biopsy

All subjects will undergo biopsy at 3 and 12 months according to protocol. The need for subsequent biopsy beyond 12 months will be at the discretion of the investigator according to standard of care. All biopsy procedures will consist of a transrectal ultrasound guided prostate biopsy with a minimum of 12 cores and include both lobes of the prostate gland. Any suspicious volumes meeting PIRADS (version 2) criteria of level 4 or 5 found on MRI will be targeted with at least 2 cores taken from each suspicious lesion. Patients will undergo pre-biopsy preparation using standard of care practices for the institution that should include the use of peri-procedural antibiotics. Patients who fail to receive antibiotics for the biopsy procedure will be considered a violation.

Anatomopathological reports will include:

1. The number and length of cores taken,

2. The number and the location of cores with cancer,
3. The cancer core length (CCL) which is linear millimeters of cancer on each core and the percentage of cancer on each core,
4. The Gleason grading of each core.

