##### ***Efficacy population***

The efficacy population will include patients who complied with the protocol for inclusion criteria and exclusion and follow-up received the appropriate dose of TOOKAD® Soluble, LDI and energy delivered and underwent the VTP procedure, receiving the ascribed dose of TOOKAD® Soluble and light, had no major protocol deviations and provided data at the 12 month biopsy. A "major" protocol deviation is defined as one which, in the opinion of the PI, could importantly influence the result of the 12 months biopsy and which is adjudicated before the 12-month biopsy.

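### Protocol 5.5.4 ends study participation, not just study treatment, after a study-related SAE or a safety-relevant violation, so the Month 12 biopsy and questionnaires can go missing selectively in harmed men

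*Protocol*

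**What the plan says.** Protocol 5.5.4 opens with "The criteria for terminating participation in the study are detailed below". Two of its five items matter here.

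- Item 1 begins "Serious adverse event that is study-related (see definition further below), as recommended by the Investigator". The same sentence continues into the rule for men with grade 3 or 4 events and treatable cancer at Month 3, who leave the study unless the IRB approves otherwise.
- Item 4 reads "Major protocol violation, defined as any violation that may impact the safety of a study subject" and carries no qualifier.

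Other relevant text:

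- Protocol 5.5.5 describes one drug administration and one light session. Protocol 6.4.10 adds a single optional re-treatment after a positive Month 3 biopsy.
- Protocol 5.5.3 restricts withdrawal at the Investigator's discretion to cases where staying in would endanger health or welfare. It adds: "Every effort must be made to follow withdrawn subjects for safety reasons using the appropriate CRFs until the planned end of the study period".
- Protocol 9.2 follows all adverse events to 60 months.
- Protocol 5.5.6 lets the Sponsor replace a man who leaves before the Month 3 biopsy, but not after it.
- Synopsis, number of patients: "In order to obtain at least 44 evaluable patients, a total of 50 patients will be included".
- SAP, Efficacy population: men must have 12-month biopsy data and no major deviation. A major deviation is one that, in the PI's opinion, "could importantly influence the result of the 12 months biopsy".
- SAP, handling of missing data: a missing Month 12 biopsy is a failure in the primary analysis.

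**The concern.** With a one-off treatment, stopping treatment and stopping observation are different acts, and 5.5.4 provides only for the second. Once VTP has been given, ending participation cannot undo exposure. It removes the man from the protocol's assessments and from any re-treatment. Safety follow-up continues under 5.5.3 and 9.2, but nothing there names the Month 12 biopsy, which is the primary endpoint, or the questionnaires to Month 60.

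The men affected are not a random subset. They had a study-related SAE or a safety-relevant violation, and the SAE exit rests on the recommendation of an investigator in an open-label trial. The questionnaires matter most in these men, because preserved urinary and erectile function is part of the case for the treatment.

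The wording is also inconsistent in two places. Section 5.5.4 is wider than the jeopardy limit in 5.5.3. And 'major' turns on subject safety in 5.5.4 but on influence on the biopsy in the SAP.

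**Working it through.** **1. The planned margin.** 50 − 44 = 6 spare men, a 12% loss: 44 / (1 − 0.12) = 50. The documents give no loss rate. The 44 itself reproduces on the SAP's inputs (null 70%, true rate 83.6%, one-sided 10%, power 80%). The normal approximation n = [(z₀.₉₀√(0.70 × 0.30) + z₀.₈₀√(0.836 × 0.164)) / 0.136]² gives 43.7, so 44. It does not reproduce at the protocol's one-sided 5%, where an exact test needs at least 61 men. That is a separate point.

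**2. What is kept for a man who exits under item 1 or 4.**

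| Data | Kept after exit? | Source |
|---|---|---|
| Adverse events to Month 60 | Yes | Protocol 5.5.3, 9.2 |
| Month 12 biopsy | Not stated | Scheduled for all in 6.4.7 and 7.1; nothing on withdrawn men |
| IPSS and IIEF | Not stated | 7.2 scores men regardless of failure or further treatment; nothing on withdrawn men |
| PSA, additional therapies | Not stated | As above |

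**3. Effect on the Month 12 rate.** Let q be the share who exit. Assume a true response of 83.6%, exit unrelated to response, and no other loss or replacement. If exits count as failures, the expected rate is 0.836 × (1 − q):

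- q = 7.6% (half of 15.2%): 0.836 × 0.924 = 77.2%
- q = 9% (grade 3 event rate in the Latin American trial, Protocol 2.2.4): 0.836 × 0.91 = 76.1%
- q = 15.2% (related-SAE rate in the European phase III trial, Protocol 2.2.4): 0.836 × 0.848 = 70.9%, close to the 70% null

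If exits are excluded instead, the estimate describes only men without such an exit, and the data cannot show whether the others responded alike. As an example, take 35 responders among 44 biopsied men (79.5%) with 6 of 50 missing. The rate in all 50 lies anywhere from 35/50 = 70.0% to 41/50 = 82.0%.

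**4. Effect on the count of 44.** P(more than 6 lost) under a Binomial(50, q), with no replacement and no other loss:

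| q | Expected lost | Expected evaluable | P(fewer than 44) |
|---|---|---|---|
| 7.6% | 3.8 | 46.2 | 8% |
| 9% | 4.5 | 45.5 | 16% |
| 15.2% | 7.6 | 42.4 | 65% |

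A small shortfall costs little power: on the SAP's basis, by the normal approximation, 80.2% at 44 men, about 78.7% at 42 and 76.9% at 40.

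**The case against.** The strongest case is that 5.5.4 will rarely bite. The SAE limb applies only on the Investigator's recommendation, and 5.5.3 confines discretionary withdrawal to jeopardy. The part of item 1 stating outright that men will be withdrawn also needs treatable cancer at Month 3 and has an IRB exception. This stands: 15.2% is an upper scenario, not a forecast, and the 9% figure counts grade 3 events rather than related SAEs.

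Replacement before the Month 3 biopsy weakens the threat to 44. Protocol 2.2.4 says most related events came during the procedure or within days of it, so many exits could be replaced. This also stands, but replacement is optional and restores the count only. It swaps a harmed man for a new one, which deepens the selection.

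A reader might infer that all outcomes are lost. The documents do not support that, because adverse events are followed to Month 60. The SAP also reports IPSS and IIEF among its safety analyses, so safety follow-up could be read to include them. It does not say so, and the biopsy remains uncovered.

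A reader might infer that leaving the study stops nothing except data collection. It also ends protocol-mandated biopsies and MRI, which may carry risk after an injury, so any fix must keep the health-and-welfare ground.

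A reader might also infer that a clinic error would end a man's participation, since Protocol 7.1 says: "Patients who fail to receive antibiotics for the biopsy procedure will be considered a violation". But 7.1 does not call this violation major, so the link to item 4 is an inference.

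Finally, in the Latin American trial 2 of 10 treated Gleason 3+4 men had no Month 6 and Month 12 biopsies because of adverse events. This shows that harm and missing biopsies can go together. The protocol does not attribute it to a withdrawal rule.

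**Conclusion.** The point holds as a cheap improvement. The protocol ends participation where only further treatment could be at issue, and nothing secures the Month 12 biopsy or questionnaires for men who exit under items 1 or 4. The main harm is selective loss. Depending on which SAP rule is applied, the Month 12 rate either omits these men or records them as failures, by up to 12.7 percentage points in the upper scenario (83.6% to 70.9%). That figure assumes that every man with a related SAE exits, that exit is unrelated to response, and that nobody is replaced.

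It would be tempting to conclude that 50 enrolled men cannot deliver 44. The documents do not support this: the chance of a shortfall runs from 8% to 65% with the assumed exit rate, before replacement and other losses, and the power cost is small.

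**What to change.** In Protocol 5.5.3 and 5.5.4, separate ending study treatment from ending data collection. State that men meeting items 1 or 4 remain in the scheduled assessments (Month 12 biopsy, IPSS and IIEF, PSA, adverse events, additional therapies) to Month 60, unless:

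- consent is withdrawn;
- the assessment would endanger health or welfare, the ground already in 5.5.3; or
- later cancer treatment makes the assessment impossible.

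Leave the re-treatment rules unchanged; no new one is needed or proposed. Reconcile the wider withdrawal wording of 5.5.4 with the limit in 5.5.3. Reconcile the two meanings of 'major' in 5.5.4 and the SAP's efficacy population, or use distinct terms. In the SAP, state one rule for how a man without a Month 12 biopsy enters the primary analysis.

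The cost is a protocol amendment with consent wording, a small SAP edit, and the continued burden on these men of visits already scheduled for everyone. No new procedure is added. The change has to be made prospectively, because a Month 12 biopsy not taken cannot be recovered.

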Subjects will fast per institutional standards before the VTP procedure in preparation for the use of anesthesia as per institutional standards. TOOKAD® Soluble VTP consists of the combination of a single, 10-minute IV infusion of TOOKAD® Soluble at the dose of 4 mg/kg, followed by the illumination of the zone to be treated with a 753-nm laser light delivered through transperineal interstitial optical fibers at a power of 150 mW/cm and light energy of 200 J/cm applied over 22 minutes and 15 seconds. Treatment for an individual patient is guided by the software TOOGUIDE TRUS, which is operated by the urologist and allows for the acquisition of TRUS images while the patient is in the treatment position, thus defining the prostate contours, the target and the optimal fiber configuration to maximize light dose in the target while sparing the surrounding tissues by allowing for a margin of at least 5 mm between the light delivery fibers and the rectal wall, the apex of the prostate, and the urethra. Fibers are then introduced into transparent catheters and positioned in the prostate areas of interest using a transperineal template. In case of unilateral disease, treatment of one lobe is applied. In case of bilateral disease, bilateral treatment is applied simultaneously or sequentially at the surgeon's discretion.

Re-treatment of lobes found positive for cancer at 3 months of follow-up is allowed. Re-treatment will be performed using the same drug and light dosing parameters as described for initial treatment and applied in the same manner. Re-treatment will be allowed 2-4 months following 3 month biopsy. Re-treatment may include either one (hemi gland) or both lobes (whole gland) of the prostate. As mentioned above, in case of signs of cancer progression on the same side or in case of treatment-related Grade 3-4 adverse events during their first treatment, patients will not be retreated and will be withdrawn and managed as per local standard of care, unless justification for continuing on study is specifically sought and approved from the IRB.

DURATION OF STUDY:

Patients will be followed until 60 months with assessment of the primary end-point at 12 month, and patients' questionnaires at 1, 3, 6 and 12 months and every 12 months until 60 months.

DURATION OF TREATMENT and STUDY PROCEDURES:

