4 TRIAL DESIGN

4.1 Overall study design and plan

This is a single center, single-arm, open-label, 60-month follow-up phase IIb clinical trial. Men with localized prostate cancer will receive TOOKAD® Soluble -VTP treatment under general anesthesia. Prior to the TOOKAD® Soluble- VTP treatment, patients will undergo routine ultrasound examination in the operating room for morphometric description of the prostate and to facilitate accurate treatment guidance for the treatment with TOOKAD® Soluble- VTP. Treatment will then be applied to the prostate gland as a focal therapy, hemiablation procedure designed to destroy the lobe of the prostate gland that contains the Gleason score 7 (3+4) cancer. Afterwards, patients will be followed for 12 months with clinical evaluation, questionnaires on QOL, erectile and urinary functions, and PSA testing. In addition, treatment outcomes will be assessed based on prostate biopsy results at 3, 12, 24, 36, 48 and 60 months after the TOOKAD® Soluble treatment. All patients will undergo biopsy at 3 and 12 months after the TOOKAD® treatment. Thereafter, biopsy will be performed for cause per institutional standards. If the Month 3 biopsy is positive for any cancer patients will be allowed a single re-treatment by TOOKAD® Soluble VTP. However, patients with evidence of clinical deterioration on the same side such as worsening Gleason score, increased core involvement with cancer tumor grades on the 3-month biopsy and/or rising PSA will be withdrawn from the study and proceed with standard care. In addition, patients who experience treatment-related Grade 3-4 adverse events during their first treatment will not be re-treated at month 3, will be withdrawn and proceed with standard care if the month-3 biopsy contains cancer on the same or contralateral side, unless justification for continuing on study is specifically sought and approved from the IRB.

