5.2 Inclusion Criteria

Subjects will be eligible for inclusion in the study if all of the following criteria are met:

1. Men over 18 years of age;
2. Patients who have had a multiparametric MRI of the prostate performed and have undergone transrectal systematic biopsy plus biopsy of any volumes considered suspicious per the MRI (PIRADS version 2 score of 4 or 5) within 6 months before signing consent;
3. Histological diagnosis of prostate cancer identifying Gleason score of 3+4 on one half of the prostate gland (right or left) in no more than 2 sextants of the prostate gland and not present in more than 50% of any one core taken systematically. The involvement criterion does not apply to cores taken from MRI suspicious volumes;
4. Patients with concomitant Gleason score 3+3 prostate cancer in less than 50% of any core at any site will be considered eligible;
5. Prostate cancer stage up to cT2a – N0/Nx – M0/Mx;
6. Prostate volume ≥ 25 mL and ≤ 70 mL;
7. Serum PSA ≤ 10 ng/mL;

8. Men who are sexually active with women of childbearing potential must use contraceptive method with a failure rate of less than 1% per year. Contraception should be continued for a period of 90 days after the VTP procedure. The individual methods of contraception may be determined in consultation with the investigator;
9. Signed Informed Consent Form.

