6.2.3 Treatment Conditions

Treatment guidance will help to determine the number and position of laser fibers to be inserted, with the length of illumination necessary to achieve a Light Density Index ≥ 1 in the targeted tissue. In case of unilateral disease, focal treatment of one lobe will be applied. In case of bilateral disease (discovered at entry or during follow-up), bilateral treatment will be applied consecutively or simultaneously. Retreatment of lobes found positive for cancer at 3-months follow-up will be allowed, provided there is no sign of cancer progression in the treated lobe and the patient did not experience grade 3 or 4 adverse events.

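### The Month 3 withdrawal wording differs between protocol sections, and the SAP conflicts on how withdrawn men count, so the same man's handling can change the primary result

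*Protocol*

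**What the plan says.** **Protocol, Month 3 withdrawal.** Section 4.1, and the synopsis under study design in the same terms, require withdrawal for clinical deterioration on the same side, "such as worsening Gleason score, increased core involvement with cancer tumor grades on the 3-month biopsy and/or rising PSA". No threshold is given for any of the three. Section 5.5.4 item 3 requires withdrawal for the same kind of deterioration, "such as Gleason grade 5 cancer, more than 2 sextants including Gleason grade 4 cancer on the treated side on the 3-month re-biopsy". It mentions neither PSA nor core involvement. Item 2 of 5.5.4 also allows withdrawal on the investigator's clinical judgment.

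**Protocol, retreatment.** Section 4.1: "If the Month 3 biopsy is positive for any cancer patients will be allowed a single re-treatment by TOOKAD® Soluble VTP". Section 6.2.3 permits it "provided there is no sign of cancer progression in the treated lobe and the patient did not experience grade 3 or 4 adverse events", with no definition of progression.

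**Protocol, IRB exception.** The synopsis under treatment conditions says of both progression and Grade 3-4 events that "unless justification for continuing on study is specifically sought and approved from the IRB" is a way to stay on study, and footnote c of the flow chart does likewise. In 4.1 the exception is attached only to the adverse-event sentence, and in 5.5.4 only to item 1. The study-design paragraph of the synopsis and section 6.2.3 have none.

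**Protocol, after withdrawal.** Men withdrawn after the Month 3 biopsy are not replaced (5.5.6). Follow-up of withdrawn men is described as being for safety (5.5.3).

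**SAP.**
- *Efficacy population* requires data from the 12-month biopsy.
- *Handling of missing data* counts a missing Month 12 biopsy as failure in the primary analysis.
- *Primary efficacy analysis* names as failures men with pattern 4 or 5 before 12 months who receive radical therapy. It sets success at a one-sided 90% lower bound of at least 70% after rounding to 0.01, that is 35 or more of 44.
- *Efficacy analysis* mentions retreated men only in a secondary analysis.

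**The concern.** The two withdrawal descriptions differ in kind. Section 4.1 measures change from baseline, while 5.5.4 item 3 gives an absolute grade and a sextant count. A man can fit the first and none of the examples in the second. He may then be withdrawn to standard care, or stay on study and be retreated, depending on the section the site follows. Where progression is the reason, the section also determines whether an IRB exception is open to him.

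The statistical stake follows from this. A withdrawn man may never have a Month 12 biopsy, while a retreated man probably will. Because the SAP gives two incompatible treatments of a man without that biopsy, an inconsistent clinical rule feeds into an unresolved analysis rule. The success threshold can turn on a single man.

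**Working it through.** **Step 1. The same man under both sections.** At entry, 3+4 disease is limited to what lies "in no more than 2 sextants of the prostate gland and not present in more than 50% of any one core taken systematically" (5.2).

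| Month 3 finding, treated side | Section 4.1 examples | Section 5.5.4 item 3 examples |
|---|---|---|
| 4+3 in one sextant | named (worsening Gleason) | not matched: no grade 5, not more than 2 sextants |
| Residual 3+3, rising PSA | named (PSA) | not matched |
| 3+4 going from one to two sextants, more core involvement | named (core involvement) | not matched: 2 is not more than 2 |

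**Step 2. How he then counts.** This assumes that a withdrawn man has no Month 12 biopsy and a retreated man has one.

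| SAP reading | If withdrawn | If kept and retreated | What can change |
|---|---|---|---|
| (i) Month 12 data required; retreated men in primary | out | own result | denominator |
| (ii) Missing biopsy is failure; retreated men in primary | failure | own result | numerator |
| (iii) Month 12 data required; retreated men not in primary | out | out | nothing |
| (iv) Missing biopsy is failure; retreated men not in primary | failure | out | denominator |

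The radical-therapy rule does not settle this. It needs both pattern 4 or 5 before 12 months and radical therapy, so the man with residual 3+3 and a rising PSA falls outside it.

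**Step 3. Reproduce the SAP rule.** The exact (Clopper-Pearson) one-sided 90% lower bound for r responders of n is the 0.10 quantile of Beta(r, n − r + 1).
- 35/44: Beta(35, 10) gives 0.696, which rounds to 0.70. Success, as the SAP states.
- 34/44: Beta(34, 11) gives 0.672. Not success.

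**Step 4. Effect of the handling.** The documents do not give the number of men on whom the sections disagree, so one and two are assumed, out of 44.

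*One man, 34 responders among the other 43:*
- withdrawn and excluded: 34/43, bound 0.690, not success;
- withdrawn and counted as failure: 34/44, bound 0.672, not success;
- kept, in the primary set and responding: 35/44, bound 0.696, rounded to 0.70, success.

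*Two men, 34 responders among the other 42:*
- withdrawn and excluded: 34/42, Beta(34, 9), bound 0.709, success;
- withdrawn and counted as failures: 34/44, bound 0.672, not success.

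The one-man case shows the effect of the withdrawal decision. The two-man case shows the effect of the SAP conflict alone.

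**Step 5. Size per man.** There is no single figure. Flipping one outcome with 44 fixed moves the rate by 1/44 = 2.3 points. Excluding a non-responder takes 34/44 (77.3%) to 34/43 (79.1%), 1.8 points. Excluding a responder takes 35/44 (79.5%) to 34/43 (79.1%), 0.5 points.

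**The case against.** The strongest reply is that there is no contradiction. Sections 4.1 and 5.5.4 apply one test, same-side clinical deterioration, and each only illustrates it. Item 2 of 5.5.4 lets the investigator withdraw any of the men in the first table. This stands in part. A reader might infer from the lead-in to 5.5.4 that it is a closed list, under which these men must be kept. The text does not support that, because item 3 gives examples and item 2 leaves room for judgment.

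The inconsistency nevertheless remains. Both sentences are mandatory, and they illustrate the test at clearly different levels. Nor is discretion a settled fallback: 5.5.3 allows investigator withdrawal only where continuing would endanger the man's health or welfare, which is narrower than item 2. The IRB exception differs between sections whichever way the examples are read.

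A reader might also infer that the mismatch necessarily changes the primary denominator, or that each affected man is a likely failure. Neither follows. The denominator moves in two of the four readings above, stays fixed in (ii), and nothing changes in (iii). A man with residual 3+3 and a rising PSA has no grade 4 or 5 and has not failed the primary endpoint at that point.

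Finally, the SAP conflict would exist even if the withdrawal wording were uniform, and the missing-biopsy rule already gives one answer. Both points are fair. But the efficacy population definition still gives the opposite answer, and the uneven withdrawal wording affects how many men fall between the two.

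**Conclusion.** The point holds as an inconsistency that can change the primary result, through the numerator or the denominator. The protocol describes Month 3 deterioration in two different ways, adds an undefined third wording, and applies the IRB exception to progression only in places. The SAP both excludes and fails a man without a Month 12 biopsy.

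One man handled differently can decide success (34/44 or 34/43 against 35/44). With two withdrawn men, the choice of SAP rule alone can decide it (34/42 against 34/44). These are illustrations under assumed numbers of affected men, with 44 men otherwise evaluable and exact bounds. They do not predict how many men are affected, which the documents do not allow one to derive. The conclusion does not depend on the separate question of the alpha level used to justify 44. It should be fixed before the primary analysis, and it does not undermine the design as a whole.

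**What to change.** **Protocol.** Reconcile the synopsis (study design, treatment conditions and flow-chart footnote c) and sections 4.1, 5.5.4 and 6.2.3 into one consistent Month 3 rule for withdrawal and retreatment, with one statement on whether the IRB exception applies to progression. Which criterion applies, and how much discretion it leaves, is for the sponsor and investigator. This review takes no view.

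**SAP.** Amend the efficacy population so that treated men withdrawn at or after the Month 3 biopsy without a Month 12 biopsy stay in the primary denominator as failures, as the missing-data section already states. In the efficacy analysis section, state whether retreated men are in the primary analysis.

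**Cost.** A protocol clarification and a short SAP amendment, with no new data collection. The reported response rate may be slightly lower than if these men were excluded.
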